7.1. Baseline Demographics

Baseline demographic variables and other relevant clinical baseline characteristics as defined in Section 6.1 will be summarised for each treatment group.

Summaries of continuous variables will be presented as means and standard deviations if data is consistent with that from a normal population distribution, and as medians and inter-quartile ranges for data that is inconsistent. Categorical variables will be presented as frequencies and percentages.

7.2. Primary Analysis

Uncorrected lower respiratory symptom scores collected from D0 to D14 will be aggregated to create an overall total for each patient. Where patient scores are missing, data will be imputed based upon rules set within Section 7.5. Patients missing $\geq 20\%$ of score data will be excluded from any additional per-protocol analyses.

Data will be presented using summary statistics per treatment group and will include median and interquartile range (IQR). A supplementary plot showing individual measurements for both groups with a box & whisker overlay showing median and IQR will be produced.

Primary analysis to test for difference between the mean aggregated scores of the two treatment groups will be carried out using Mann-Whitney U tests. Differences will be considered significant at $P < 0.05$. All P values are two-sided.

An additional secondary analysis will take place correcting the scores for bronchoscopy-related symptoms. Full methodology will be clarified within Section 7.3.1 below.

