4.4. Sample Size

An overall population size of 44 asthmatic subjects was based on the following assumptions:

- Type I error probability $\alpha = 5\%$
- Effect size = $(\mu_1 - \mu_0) / \sigma$
 - μ_i = mean PEP in group i ($i=1$: OC459, $i=0$: placebo),
 - σ = standard deviation of PEP
- PEP is primary end-point (=total daily lower respiratory symptom scores over D0 to D14, potential maximum of 315).

Based on a previously completed trial with similar design conducted at the same study site [10], σ is estimated to be 21.15 and the effect size equal to 22.21, yielding $n=15$ evaluable subjects per treatment group at 80% power. This is grossed-up for 80% rhinovirus inoculation success and adjusted for expected drop-outs to yield 22 enrolled patients per treatment group.

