4.7. Withdrawal and Replacement

Subjects who are considered evaluable (confirmed rhinovirus infection) and have completed at least 14 days post inoculation with RV-16 will be included in the analysis. Subjects lost to follow up will not be replaced if they were evaluable with sufficient data to assess the primary outcome. Subjects who are either withdrawn from the trial or who chose to discontinue participation and do not meet these criteria will be replaced until a sufficient number of evaluable subjects are reached (n=30).

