4.10. Study Baseline

For Primary and Secondary endpoint assessments, baseline will be determined as the last measurement taken prior to virus inoculation i.e. Day 0 (ACQ-6, home PEFR, home FEV1, clinic FEV1, clinic FVC, FeNO, virus load, soluble mediators) where available. If/where this is missing, the value on the previous visit will be used, for example, laboratory bloods and PC20 (for laboratory bloods, the sample on day -8 will be taken as a baseline, for PC20, the result from day -9 will be taken).

Demographic baseline variables will be taken at Screening, Day -21 and Day 0 (where available).

5. Analysis Sets

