6.2. Primary Analysis Variable

- The primary endpoint will consist of the sum of uncorrected lower respiratory symptom scores from day 0 to day 14. Daily scores will be out of 21 (seven symptom questions rated from zero to three) creating a potential maximum total score of 315.

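### The primary test makes no use of the pre-dose ACQ-6 already collected, and no between-arm estimate with a confidence interval is planned; the power at stake depends on a correlation the documents do not give

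*SAP*

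**What the plan says.** SAP 7.2 fixes the primary analysis in one sentence: "Primary analysis to test for difference between the mean aggregated scores of the two treatment groups will be carried out using Mann-Whitney U tests". It adds that "All P values are two-sided". SAP 6.2 defines the quantity tested as the "sum of uncorrected lower respiratory symptom scores from day 0 to day 14", so nothing is subtracted for symptoms present before inoculation. No covariate is named in SAP 7.2 or Protocol 10.2. SAP 4.6 randomises in blocks of four with no stratification factor.

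The planned output is per arm. Shell Table 2.02 has n, mean, SD, median, minimum, maximum and IQR, by day and in total. Table 2.01 lists every subject's scores, and a box plot shows individual values. Table 2.03 holds the test result, under a heading that counts points above the median, which belongs to a median test. None of these contains a between-arm difference, a Hodges-Lehmann shift or a confidence interval.

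The schedule in SAP 4.9 records the ACQ at screening and at Visit 1 (Day -21). SAP 6.1 puts the Day -21 ACQ-6 in a supplementary table by arm. The SAP's own baseline is a different time point. SAP 4.10 says that "baseline will be determined as the last measurement taken prior to virus inoculation i.e. Day 0", which comes after 21 days of study drug.

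**The concern.** Entry requires an ACQ above 0.75, so subjects bring stable asthma symptoms into an uncorrected 15-day total. Those symptoms add between-subject variation unrelated to treatment. With about 15 per arm and no stratification, a chance difference in severity passes straight into the comparison. The analysed subjects are also limited to those infected and followed for 14 days (SAP 5.2), so blocking at randomisation does not guarantee balance among them. A pre-dose covariate could remove part of that variation at no cost in patients.

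Separately, a P value without an interval does not tell the reader which effects a non-significant result rules out. The description of the test is also wrong: Mann-Whitney compares the two distributions through ranks and does not test a difference in means.

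**Working it through.** **Inputs.** SAP 4.4 gives the SD and difference ("is estimated to be 21.15 and the effect size equal to 22.21") and 15 "evaluable subjects per treatment group at 80% power". Alpha is 5%, two-sided. SAP 4.7 replaces subjects until 30 are evaluable. The 22.21 is labelled an effect size but can only be a raw difference: read as SD units it would need 1 subject per arm. The standardised difference is 22.21/21.15 = 1.05. The correlation r between pre-dose severity and the total is not in either document, so r = 0 to 0.7 is an assumption.

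**The plan's own figure.** n per arm = 2 × [(1.960 + 0.842) × 21.15/22.21]² = 14.24, rounded up to 15. This reproduces.

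**Is there a valid covariate?** Protocol 9.1 places baseline investigations and randomisation before the run-in on study drug, and the ACQ asks about the past week. Day -21 ACQ-6 therefore describes the period before dosing. Day 0 values do not. The diary starts on Day -21 (Protocol 9.4), the first dosing day, so there is no multi-day pre-dose symptom score.

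**Power at 15 per arm.** Simulated with normal data, difference 22.21, SD 21.15, two-sided 5%. Adjustment reduces the SD to 21.15 × √(1 − r²).

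| Assumed r | Mann-Whitney | Rank ANCOVA | Unadjusted t-test | ANCOVA |
|---|---|---|---|---|
| 0 | 76% | 76% | 79–80% | 78% |
| 0.2 | 76% | 78% | 79–80% | 80% |
| 0.3 | 76% | 79% | 79–80% | 81% |
| 0.5 | 76% | 85% | 79–80% | 88% |
| 0.7 | 76% | 95% | 79–80% | 97% |

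Figures are rounded; separate runs agree to within about one point. Rank methods should be compared with Mann-Whitney, and ANCOVA with the t-test. Setting ANCOVA against Mann-Whitney would mix the change of test with the effect of adjustment. In 10,000 null runs per setting with normal data, rejection was between 4.1% and 5.2% for Mann-Whitney, rank ANCOVA and ANCOVA.

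**The same gain as sample size.** 14.24 × (1 − r²) gives 13.67, 12.95, 10.68 and 7.26 at r = 0.2, 0.3, 0.5 and 0.7, or 14, 13, 11 and 8 per arm.

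**Chance imbalance.** The SD of the between-arm difference in a standardised covariate is √(2/15) = 0.365. A difference above 0.5 SD either way is 0.5/0.365 = 1.37 standard errors, a probability of about 17%. At r = 0.5 it would move the result by 0.5 × 0.5 × 21.15 = 5.3 points, 24% of 22.21.

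**Interval.** The unadjusted 95% half-width is 2.048 × 21.15 × √(2/15) = 15.8 points. With one covariate it is 15.1, 13.7 and 11.3 at r = 0.3, 0.5 and 0.7. On the unadjusted figure, an observed benefit of 10 points gives −5.8 to 25.8, which still includes 22.21. An observed benefit of 0 gives ±15.8, which excludes it. The dividing line is 22.21 − 15.8 = 6.4 points. Both results would be reported as P > 0.05.

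**The case against.** An unadjusted, prespecified, two-sided rank test is valid and controls type I error, including the part due to chance imbalance. The sample size reproduces. Adjustment is therefore a gain in efficiency and corrects no error. This stands.

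A reader might infer that the plan demonstrably wastes power. The documents do not support that, because neither gives a correlation. SAP 7.4.3 relates ACQ-6 to symptom sums over the same week, which says little about prediction from three weeks before inoculation. Restricting entry to ACQ above 0.75 may weaken the correlation further. The power figures also assume normal data. In lognormal runs (assumed placebo mean 40, SD 21.15, proportional effect), Mann-Whitney power was already 98–99%, leaving little to gain.

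A reader might also infer that severity data are ignored, or that a null result could not be interpreted at all. Neither follows. Day -21 ACQ-6 is tabulated by arm, so imbalance would be visible. Table 2.02 gives means and SDs, from which a mean difference and t-based interval can be worked out. What is missing is a prespecified interval in the output, and any use of the covariate in the primary test.

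The secondary analyses of change from Day 0 (SAP 7.3.1) deal in part with stable symptoms. Their baseline follows 21 days of dosing, so subtracting it could remove part of any drug effect during the run-in.

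**Conclusion.** The point holds as one of efficiency and reporting; the primary test is valid and 15 per arm is not in dispute. Three gaps can be read directly from the SAP: no pre-dose covariate in the primary test, no planned between-arm estimate or confidence interval, and a description of Mann-Whitney as a test of means.

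The missing interval matters whatever the correlation. At the planned SD its half-width is about 15.8 points, which decides whether a non-significant result excludes the planned 22.21.

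The value of adjustment is conditional. Under normal data, rank ANCOVA adds about 2 points of power or less at r of 0.2 or below, about 3 at 0.3, 9 at 0.5 and 19 at 0.7, and loses nothing at 0. Parametric ANCOVA loses about a point against the t-test at r = 0 and gains little until r is near 0.5. All figures assume 15 evaluable subjects per arm and the planned difference and SD.

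**What to change.** Before unblinding, amend SAP 7.2 and its shells as follows.

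- Make the primary test a rank ANCOVA (Quade) of the Day 0 to 14 total on Day -21 ACQ-6.
- Keep the unadjusted Mann-Whitney test as supportive, with its Hodges-Lehmann shift and 95% CI. That shift belongs to Mann-Whitney; Quade's test gives a P value and no estimate.
- Report the ANCOVA-adjusted mean difference with 95% CI as the covariate-adjusted estimate. State in advance that it comes from a different model, so its interval need not agree exactly with the rank P value.
- Do not use Day 0 or run-in diary values as the covariate. If Day -21 ACQ-6 is missing, apply the same rule in both arms; the screening ACQ is also pre-dose.
- Replace the reference to means with wording that matches the test, and relabel Table 2.03 for a rank-sum test.

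The cost is SAP text, revised shells and one extra program. No further visit, sample or subject is needed.

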7.3. Secondary Analysis

7.3.1. Secondary Efficacy Analysis

Lower respiratory symptom scores collected from D0 to D14 will be corrected for the effects of bronchoscopy by subtracting the baseline symptoms value (mean average of values from D-13 to D-9) from the two days affected by bronchoscopy symptoms (day -8 and day -7). The adjusted residual symptom scores for day -8 and day -7 (which we assume to be purely bronchoscopy related) would then be subtracted from day 5 and day 6 to complete the correction.

Analysis to test for difference between the mean aggregated corrected scores of the two treatment groups will be carried out using Mann-Whitney U tests.

The effect of the drug on asthma exacerbations (as defined by change from day 0 to peak infection in symptoms, lung function, and measures of lung inflammation) will be using presented summary statistics per treatment group and will include median and interquartile range (IQR). Within-subject differences will be analysed using ANOVA and 2-tailed paired Student's t-tests or Wilcoxon signed rank test in the event where data is not consistent with a normal population distribution. Analysis to determine the difference in effect of OC459 and placebo will be performed using unpaired (two-sample) t-test or Mann-Whitney U tests for data not consistent with a normal population distribution at each phase of the study.

Differences will be considered significant at $P < 0.05$ within a hierarchy of the primary outcome, and interpreted more cautiously for secondary efficacy outcomes, (likewise more so for

exploratory outcomes). Patients missing $\geq 20\%$ of endpoint data will be excluded from any additional per-protocol analyses. Analyses that are conducted using the Per Protocol analysis set that are in agreement with conclusions derived from the Full analysis set will be more strongly interpreted than those in disagreement. All P values are two-sided.

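### The primary analysis is described as a test of mean scores, but Mann-Whitney does not establish a mean difference, and no between-arm estimate or confidence interval is planned

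*SAP*

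**What the plan says.** SAP 6.2 defines the endpoint: "The primary endpoint will consist of the sum of uncorrected lower respiratory symptom scores from day 0 to day 14", with a possible maximum of 315. SAP 7.2 names hypothesis and test together: the primary analysis to "test for difference between the mean aggregated scores of the two treatment groups will be carried out using Mann-Whitney U tests", at P < 0.05, and "All P values are two-sided". SAP 7.3.1 uses the same form for the bronchoscopy-corrected total: "Analysis to test for difference between the mean aggregated corrected scores of the two treatment groups will be carried out using Mann-Whitney U tests".

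SAP 4.4, like protocol 10.1, defines the effect through "mean PEP in group i" and states that "σ is estimated to be 21.15 and the effect size equal to 22.21, yielding $n=15$ evaluable subjects per treatment group at 80% power".

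For reporting, SAP 7.2 plans medians, interquartile ranges and a box plot by group. Shell Table 2.02 (SAP Appendix B) adds each group's mean and SD. Shell Table 2.03 gives test statistics and p-values only. Protocol 10.2 leaves the between-group test open, as parametric or non-parametric.

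**The concern.** The plan uses one parameter for sizing and for wording the hypothesis, the difference in means, and then applies a test of something else. The Mann-Whitney reference distribution assumes that both arms share one distribution, and the statistic estimates P(OC459 total < placebo total). Equality of means and P = 0.5 are the same hypothesis if the drug only shifts the distribution. If it also changes the shape, they can part. A total bounded at 0, and a drug meant to prevent or attenuate deterioration, make a change of shape plausible.

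Two things are at stake. A report that follows the SAP's wording could claim a difference in means that the test has not shown. And whatever the p-value, the reader would have no estimate of how large the difference between arms is or how uncertain it is. With about 15 evaluable subjects per arm, that estimate matters at least as much as the p-value.

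**Working it through.** **Inputs.** From SAP 4.4: SD 21.15, difference 22.21, alpha 5%, power 80%, 15 evaluable per arm. From SAP 7.2: two-sided tests. The documents give no placebo mean and no distribution shape, so every shape below is an assumption.

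**1. What the trial was sized on.** The figure 22.21 is labelled an effect size but works only as a raw difference; as a standardised effect it would give n = 1. Standardised, it is 22.21/21.15 = 1.05. For a two-sided comparison of two means:

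n per arm = 2 × (1.960 + 0.842)² × (21.15/22.21)² = 2 × 7.849 × 0.9068 = 14.2, rounded up to 15.

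This reproduces the stated 15. A one-sided test would give 12. By the noncentral t distribution, 15 per arm gives 79.3% power. The sizing is therefore a two-sided comparison of means with a common SD.

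**2. Cost of Mann-Whitney under that same model.** In 40,000 simulated trials with normal scores and a shift of 22.21, Mann-Whitney had about 76% power at 15 per arm, 79.1% at 16 and 82.0% at 17. The relative-efficiency approximation agrees: 16/(3/π) = 16.8. The cost is about 3 percentage points, or one to two subjects per arm.

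**3. No drug effect.** With identical distributions in both arms, Mann-Whitney rejected in 4.5% to 4.7% of trials. Rejection rates using the exact cut-off matched the large-sample test wherever both were run.

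**4. Equal means, unequal shapes (15 per arm).**

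| Assumed shapes | Mann-Whitney rejects | t-test rejects |
|---|---|---|
| Normal, SD ratio 2 | 5.3% | 5.3% |
| Gamma, both means 40, SD 21.15 v half that | 7.5% | 5.9% |
| Gamma, both means 20, SD 21.15 v half that | 14.4% | 6.8% |
| Equal mean and SD, opposite skew | 14% to 24% | 7% to 9% |

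In the third row the medians are about 13.2 and 18.2 although the means are equal. Mann-Whitney is correctly detecting that the distributions differ. It is not showing a difference in means.

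**5. Mean difference of 22.21, pooled SD 21.15, 15 per arm.**

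| Form of the effect | Mann-Whitney power | t-test power |
|---|---|---|
| Normal shift | 76% | 79% |
| Gamma shift (mean 30 before the shift) | 85.8% | 79.9% |
| Lognormal shift (mean 30 before the shift) | 92.2% | 81.0% |
| Benefit confined to 50% of subjects | 64.8% | 79.4% |
| Benefit confined to 40% of subjects | 46.7% | 81.2% |

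The choice of test can help or hurt, depending on a shape that the documents do not give.

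**6. What would be reported.** SAP 7.2 and shell Tables 2.02 and 2.03 contain group summaries and p-values. None contains a difference between arms, a Hodges-Lehmann shift, P(OC459 < placebo), or a confidence interval for any of these.

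**The case against.** The strongest reply is that "mean" is one loose word. The objective and endpoint speak of the total score without naming a mean, the test is fixed in advance, and the planned summaries are medians and interquartile ranges. Sizing on a t-test and analysing by Mann-Whitney is common and costs about 3 points here. With skewed scores Mann-Whitney is a sensible choice. All of this stands, and it is why the test should stay. But the word also appears in SAP 7.3.1, it is the quantity behind SAP 4.4, and the reply does not supply the missing estimate and interval.

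A reader might infer that the primary test has an inflated type I error. The documents do not support that. In a randomised placebo comparison, no drug effect means identical distributions, and there the test holds its level. The higher rates in step 4 arise where the drug does change the distribution, so rejecting "no effect" is correct; only the conclusion about means is not.

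A reader might also infer that the trial is likely to miss a real benefit in the severe tail. That depends on what is assumed. With the planned difference arising from a severe 35% of placebo subjects, power is 37% for Mann-Whitney against 66% for a test of means if the OC459 mean is 20, but 33% against 47% if it is 40. With a proportional reduction at the planned difference and SD (assumed placebo means of 40 to 60), the two tests are within about 4 points of each other.

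Nor would a switch to a t-test settle the matter: at 15 per arm the Welch test also drifts to 5.6% to 6.7% in the equal-mean gamma cases.

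**Conclusion.** The mismatch is real and limited in size. As written, the plan would let a significant Mann-Whitney result be stated as a difference in means. That does not follow unless a location shift, or some comparable restriction on how the drug acts, is assumed, and the plan assumes none. The plan also provides no between-arm effect measure or interval for the primary endpoint. Validity under no drug effect is sound, and the power cost under the design's own model is about 3 points. Larger gains or losses rest on assumed shapes and run in both directions, so they are no argument against the test. This should be corrected before unblinding; it does not put the design in doubt.

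**What to change.** Keep Mann-Whitney as the primary test.

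- **Wording.** In SAP 7.2 and 7.3.1, replace the reference to a difference between mean aggregated scores with a difference between the distributions of aggregated scores (a tendency to lower or higher totals). State that the result will be reported in those terms.
- **Matching estimate.** Add the Hodges-Lehmann shift, or P(OC459 < placebo), with a 95% CI.
- **Supportive estimate.** Add the difference in means with a 95% CI (Welch or permutation-based), stated to have no confirmatory role. This reports the quantity used in SAP 4.4. Giving an estimate rather than a second p-value avoids needing a rule for two tests that disagree.
- **Shell.** While editing, reconcile shell Table 2.03: its title names Mann-Whitney, but its column heading describes counts above the median, which belong to a median test. Add the two estimates there.

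The cost is a few sentences and a minor extra analysis of data already collected. The small downside is that the primary claim is worded less directly.

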7.3. Secondary Analysis

7.3.1. Secondary Efficacy Analysis

Lower respiratory symptom scores collected from D0 to D14 will be corrected for the effects of bronchoscopy by subtracting the baseline symptoms value (mean average of values from D-13 to D-9) from the two days affected by bronchoscopy symptoms (day -8 and day -7). The adjusted residual symptom scores for day -8 and day -7 (which we assume to be purely bronchoscopy related) would then be subtracted from day 5 and day 6 to complete the correction.

Analysis to test for difference between the mean aggregated corrected scores of the two treatment groups will be carried out using Mann-Whitney U tests.

The effect of the drug on asthma exacerbations (as defined by change from day 0 to peak infection in symptoms, lung function, and measures of lung inflammation) will be using presented summary statistics per treatment group and will include median and interquartile range (IQR). Within-subject differences will be analysed using ANOVA and 2-tailed paired Student's t-tests or Wilcoxon signed rank test in the event where data is not consistent with a normal population distribution. Analysis to determine the difference in effect of OC459 and placebo will be performed using unpaired (two-sample) t-test or Mann-Whitney U tests for data not consistent with a normal population distribution at each phase of the study.

Differences will be considered significant at $P < 0.05$ within a hierarchy of the primary outcome, and interpreted more cautiously for secondary efficacy outcomes, (likewise more so for

exploratory outcomes). Patients missing $\geq 20\%$ of endpoint data will be excluded from any additional per-protocol analyses. Analyses that are conducted using the Per Protocol analysis set that are in agreement with conclusions derived from the Full analysis set will be more strongly interpreted than those in disagreement. All P values are two-sided.

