9.4 CLINICAL SYMPTOM SCORES (INCLUDING ACQ)

Patients will be required to keep a diary card of both upper and lower respiratory tract symptoms during the study period (see Appendices). The diary cards will be commenced 21 days prior to inoculation (on day -21) to derive a baseline symptom score. Symptom scores will be kept daily for 6 weeks post-inoculation until the convalescent visit. Spirometry measurements and drug compliance will be recorded on the same diary cards.

Upper Respiratory Tract Symptoms

The diary card of upper respiratory tract symptoms will be started 21 days prior to inoculation. A total upper respiratory clinical symptom score will be derived using a scale of 0 to 3 (absent, mild, moderate and severe) for each of the following eight respiratory symptoms: sneezing, headache, malaise, fever/chills, nasal discharge, nasal obstruction, sore throat and cough, according to previously established criteria [23]. Symptoms will be recorded at the same time of day and before any procedures such as bronchoscopy are performed. An example is shown below:

Symptom	Day 1	Day 2	Day 3	Day 4	Day 5	Day 6	Day 7
Sneezing							
Headache							
Malaise							

Fever/chills							
Nasal discharge							
Nasal obstruction							
Sore throat							
Cough							
Total score							

0 = absent, 1 = mild, 2 = moderate, 3 = severe

The maximum clinical severity score on any one day would be 24. Individual symptom scores will be accumulated over the six-day period from the onset of the cold and the recording on the day prior to inoculation subtracted. Thus, for a patient who has a score of zero on day -1 prior to inoculation, the maximum cumulative score for the six days is 144.

Lower Respiratory Tract Symptoms

A diary card of lower respiratory tract symptoms will be completed with a scoring system as outlined below:

Symptom	Day 1	Day 2	Day 3	Day 4	Day 5	Day 6	Day 7
Cough on waking							
Wheeze on waking							
Daytime cough							
Daytime wheeze							
Daytime breathlessness							
Nocturnal cough, wheeze, breathlessness							
Total score							

0 = absent, 1 = mild, 2 = moderate, 3 = severe

An exacerbation of asthma is defined as an increase in the total respiratory score of at least 2 points over baseline on 2 consecutive days.

Asthma Control Questionnaire (ACQ)

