4.9. Schedule of Time and Events

Table 1: Schedule of Visits and Events

	Screening visit 1	Screening visit 2	Visit 1 (baseline)	Visit 2	Visit 3	Visit 4	Visit 5	Visit 6	Visit 7	Visit 8	Visit 9	Visit 10	Visit 11
Study day			-21	-9	-8	0	2	3	4	5	7	10	42
Ideal weekday			F	W	T	F	Su	M	T	W	F	M	F
Visit length	30 min	60 min	60 min	45 min	3 hr	60 min	45 min	45 min	45 min	3 hr	60 min	45 min	30 min
Skin prick test	X												
Viral serology	X												X
Asthma Control Questionnaire (ACQ)	X		X	X		X						X	X
Spirometry (in clinic)	X		X	X		X	X	X	X	X	X	X	X
Histamine challenge (PC ₂₀)		X	X	X							X		
Exhaled nitric oxide (FeNO)		X	X	X		X		X		X	X	X	X
Blood tests		X	X		X			X		X		X	X
ECG		X											
Urine pregnancy test		X											
Chest radiograph		X											
IMP or placebo administration			Daily from day -21 → day 14 (then stop)										
Nasosorption			X			X	X	X	X	X	X	X	X
Nasal lavage			X			X	X	X	X	X	X	X	
Nasal scrape			X		X			X		X			
Bronchoscopy (bronchosorption, BAL, brushings, biopsies)					X					X			
Sputum induction			X	X					X		X		
Virus inoculation						X							
Symptom diaries including spirometry and medication			Daily at home during study period →										
Spirometry (portable, at home)			Daily at home during study period →										

Table 2: Schedule of Treatment and Events

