7.3.2. Secondary Mechanistic Analysis

Soluble Mediators:

A total of 32 mediators in nasal samples (taken at day -21, 0, 2, 3, 4, 5, 7, 10) and bronchoscopic samples (taken at day -8, day 5) will be measured for each subject.

Values of soluble mediators obtained from bronchial samples will be presented using summary statistics per treatment group and visit. An additional table will summarise per treatment group (for each mediator) the difference in values between mediators taken at D-8 and D5. Analysis to investigate any difference in effect of OC459 and placebo for each mediator will be performed using the difference in values via unpaired (two-sample) t-test or Mann-Whitney U tests for non-parametric data.

Values of soluble mediators obtained from nasal samples will be presented using summary statistics per treatment group and visit. An additional table will summarize per treatment group (for each mediator) the difference between D-21 and peak value (the highest value measured between D0 and D10).

Taking the difference between D-21 and peak value, analysis to determine the difference in effect of OC459 and placebo for each mediator will be performed using unpaired (two-sample) t-test or Mann-Whitney U tests for non-parametric data.

Differences will be considered significant at $P < 0.05$ within a hierarchy of the primary outcome, and interpreted more cautiously for secondary efficacy outcomes, (likewise more so for exploratory outcomes). All P values are two-sided.

Leukocyte numbers:

Values of leukocyte numbers obtained from bronchial samples / flow cytometry will be presented using summary statistics per treatment group and visit. An additional table will summarise per treatment group (for each cell type) the difference in values between samples taken at D-8 and D5. Analysis to investigate any difference in effect of OC459 and placebo for each cell type will be performed using the difference in values via unpaired (two-sample) t-test or Mann-Whitney U tests for non-parametric data.

Eosinophil counts:

Values of blood and sputum eosinophilia will be presented using summary statistics per treatment group and visit. Analysis to investigate any difference in effect of OC459 and placebo for blood and sputum eosinophilia will be performed using the difference in values via unpaired (two-sample) t-test or Mann-Whitney U tests for non-parametric data.

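### If the protocol's rule that symptoms are scored before bronchoscopy covers the lower respiratory score, the bronchoscopy correction in SAP 7.3.1 is one day out of alignment

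*SAP*

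**What the plan says.** The correction in SAP 7.3.1 has two steps. It begins by "subtracting the baseline symptoms value (mean average of values from D-13 to D-9", and this is taken "from the two days affected by bronchoscopy symptoms (day -8 and day -7". Then "The adjusted residual symptom scores for day -8 and day -7 (which we assume to be purely bronchoscopy related) would then be subtracted from day"; the targets are Days 5 and 6.

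The schedule in SAP 4.9 puts bronchoscopy at Visits 3 and 8, which are Days -8 and 5. SAP 7.3.2 agrees: "bronchoscopic samples (taken at day -8, day 5".

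On diary timing, Protocol 9.4 states: "Symptoms will be recorded at the same time of day and before any procedures such as bronchoscopy are performed". The sentence is printed under the upper respiratory sub-heading. The lower respiratory sub-section introduces its grid with "A diary card of lower respiratory tract symptoms will be completed with a scoring system as outlined below" and gives no time of day. Section 9.4 opens by describing one card for both scores: "Patients will be required to keep a diary card of both upper and lower respiratory tract symptoms during the study period (see Appendices". The card in Protocol Appendix B has one column per date, with the cold score and the chest score in the same column.

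The corrected score is a listed secondary endpoint (SAP 3.2), with its own Mann-Whitney test (SAP 7.3.1) and Tables 3.01 and 3.02. The primary endpoint is the uncorrected total (SAP 6.2 and 7.2).

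**The concern.** An entry made before a bronchoscopy cannot record symptoms caused by it. Under the Protocol 9.4 rule, the first entry that could show an effect of the Day -8 procedure is Day -7, and the first that could show an effect of the Day 5 procedure is Day 6. SAP 7.3.1 nevertheless treats the Day -8 residual as wholly due to bronchoscopy and takes it off an infection day.

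At stake is whether the corrected score does its job. The second bronchoscopy falls inside the Day 0 to Day 14 window of the primary endpoint, and the corrected score is the adjustment that the SAP specifies for it. If the days are misaligned, a comparison of corrected with uncorrected results says less about bronchoscopy than it appears to.

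**Working it through.** **The plan's own figures (context only).** The maximum score is 7 items x 3 points x 15 days = 315, as in SAP 6.2. For sample size, reading 22.21 as a raw score difference with SD 21.15, two-sided alpha 0.05 and 80% power, n = 2 x [21.15 x (1.960 + 0.842) / 22.21]^2 = 14.24, rounded up to 15 per arm. This matches SAP 4.4. Normal-approximation power at 15 per arm is 82.0% (79.3% from the t distribution). Nothing here disputes these figures.

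**Which entries can carry bronchoscopy symptoms.** The SAP's own duration of two affected days is carried over.

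| | First procedure | Second procedure |
|---|---|---|
| Day of bronchoscopy | -8 | 5 |
| Days used in SAP 7.3.1 | -8, -7 | 5, 6 |
| First two affected entries, scored before the procedure | -7, -6 | 6, 7 |
| First two affected entries, scored after it or at day's end | -8, -7 | 5, 6 |

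The SAP days fit the last row and miss the third by one day.

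**What the correction removes if scoring comes first.** Let b1 and b2 be the points that bronchoscopy adds to the first and second entries after it. The documents give neither, so both are assumed.

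- Contamination of the Day 0 to 14 total: b1 (Day 6) + b2 (Day 7).
- Expected Day -8 residual: 0 from bronchoscopy.
- Expected Day -7 residual: b1.
- Removed: 0 + b1. Left in: b2.
- With Day -7/-6 residuals taken from Days 6/7, removed: b1 + b2. Left in: 0.

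| b1 | b2 | Contamination | Left by SAP rule | Left after shift |
|---|---|---|---|---|
| 3 | 0 | 3 | 0 | 0 |
| 3 | 1 | 4 | 1 | 0 |
| 3 | 2 | 5 | 2 | 0 |
| 3 | 3 | 6 | 3 | 0 |

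A simulation of 400,000 subjects with a daily SD of 2 agreed with every row to within 0.02 points.

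**Noise.** Let w be the within-subject daily SD, with independent daily errors. It is not in the documents; 1 to 3 points is assumed.

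- One residual over a five-day mean: SD = w x sqrt(1 + 1/5) = w x sqrt(1.2), which is 1.10, 2.19 and 3.29 for w = 1, 2 and 3.
- Sum of two residuals sharing that mean: variance = 2w^2 + 4w^2/5 = 2.8w^2, so SD = 1.67, 3.35 and 5.02.
- Added to the planning SD, sqrt(21.15^2 + 2.8w^2) = 21.22, 21.41 and 21.74. As an illustration, normal-approximation power at 15 per arm goes from 82.0% to 81.8%, 81.1% and 79.9%.

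The shifted correction also sums two residuals over the same mean, so its SD is the same w x sqrt(2.8). Moving the days changes what is removed and does not change precision.

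**Flooring residuals at zero.** With no bronchoscopy effect, an unfloored residual averages zero. Under a normal approximation, a floored one averages 0.40 x its SD: 0.40 x 1.10 = 0.44, 0.40 x 2.19 = 0.88 and 0.40 x 3.29 = 1.32 points per corrected day, for w = 1, 2 and 3. Flooring therefore over-corrects.

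**The case against.** The strongest reply is that the protocol does not state the timing rule for the lower score. The sentence sits in the upper respiratory sub-section, and the lower sub-section has none. Several lower items ask about daytime symptoms, which are naturally scored late in the day, and the card has morning and evening spirometry rows. With end-of-day scoring, the days in SAP 7.3.1 are right. This stands: the misalignment is conditional. But neither document says that lower scores are taken at day's end, and a shared dated card with one stated time makes the contrary reading reasonable. The text needs settling either way.

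Stronger readings are tempting, and the documents do not support them:

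- *The correction removes only half the contamination.* That needs b1 = b2. No decay pattern is given, and if the second entry is unaffected, nothing is left on Day 7.
- *The Day -8 residual is pure noise.* Sputum induction is scheduled on Day -9 and on Day 4, so a Day -8 after-effect has a partial counterpart on Day 5. The match is incomplete, because Day -9 also has a histamine challenge and Day 4 does not. Neither after-effect is the bronchoscopy effect that the SAP assumes.
- *The corrected score is the only check on bronchoscopy, so the comparison cannot be interpreted.* Tables 2.01 and 2.02 and Figure 2.05 show daily scores, so a rise around Days 5 to 7 would be visible without any correction.

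**Conclusion.** The concern holds conditionally. If the Protocol 9.4 timing rule covers the lower respiratory score, SAP 7.3.1 is misaligned by one day. Its Day -8 term removes no bronchoscopy effect from Day 5, and whatever bronchoscopy adds to the Day 7 entry stays in. In the assumed cases this is 0 to 3 points per subject, on a total with a planning SD of 21.15.

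The consequence is confined to the secondary corrected score. A reader might infer that the primary result or the treatment comparison is biased. The primary analysis uses uncorrected scores and is unaffected, and if bronchoscopy effects are equal across arms, the misalignment creates no between-arm bias. Nor is this a power problem: the assumed noise costs about 0.2 to 2 percentage points on the illustration above, and the aligned correction costs the same. The defect is that a stated correction may not correct what it claims to.

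This rests on the inference from the shared card, on the SAP's two-day duration of effect, and on assumed values for b1, b2 and w.

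**What to change.** Before unblinding, state when on a bronchoscopy day the lower respiratory score is recorded, and reconcile Protocol 9.4 with SAP 7.3.1.

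- If lower scores are recorded before procedures: subtract the Day -7 and Day -6 residuals (over the same Day -13 to -9 mean) from Days 6 and 7, and keep the present Day -8/-7 to Day 5/6 mapping as a sensitivity analysis.
- If they are recorded after the procedure or at the end of the day: correct Protocol 9.4 and keep the present days.

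In either case, do not floor residuals at zero.

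The cost is a sentence or two of text and, in the first case, one extra sensitivity analysis. The diary is daily, so no new data are needed. The change corrects alignment and brings no gain in precision.
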